4.9.3 Primary Efficacy Endpoint Analysis

The primary efficacy endpoint for Phase 2a is the ORR per RECIST 1.1 and iRECIST as determined by the Investigator.

ORR per RECIST 1.1 is defined as the proportion of subjects with confirmed CR or confirmed PR as BOR in efficacy evaluable analysis set.

iORR per iRECIST is defined as the proportion of subjects with iCR or iPR as BOR in efficacy evaluable analysis set.

Exact two-sided 95% CIs for the ORR/iORR will be calculated using Clopper-Pearson method.

A test from the Simon minimax design for null hypothesis ORR/iORR proportion 4% vs alternative hypothesis 21% will be conducted in each Phase 2a Arm: Arm I, II, III, IV, IVa, V, and Va at 1-sided alpha = 0.025 and the p-value reported.

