### 15.1. Sample Size and Power Calculation

ORR assessed by RECIST 1.1 and iRECIST will be considered as primary efficacy endpoints in each Phase 2a arm and estimated using exact confidence intervals based on the binomial distribution (Clopper-Pearson intervals) from the evaluable subjects for selected arms. All subjects treated on study and with data available for the calculation of the primary endpoint ORR will be considered evaluable. A test from the Simon minimax design for null hypothesis ORR proportion in the arm population 4% vs alternative hypothesis 21% will be conducted in selected arms at 1-sided alpha = 0.025 and the p-value reported.

Arms I, II, III, IV, and V of the Phase 2a study stage will follow the Simon's two-stage minimax design. Each arm will enroll 17 evaluable subjects in Stage 1 and, if the Go/No Go criterion is met, an additional 8 evaluable subjects in Stage 2 for a total of 25 evaluable subjects/arm. This will provide an estimated 80% power per selected arm in the Phase 2a stage of the study for the primary hypothesis test using the Simon minimax design. Exact 95% binomial Clopper-Pearson confidence interval estimates of ORR from each arm is planned to support the primary hypothesis tests.

Enrolment of up to 30 subjects per arm is planned to account for non-evaluable subjects and dropouts. Up to 238 subjects (up to 18 subjects in the Phase 1b, up to 210 subjects in all arms of Phase 2a and up to 10 subjects in the Biomarker Cohort) are planned to be enrolled in the study.

It has been reported that approximate 7% of pseudo-progression occurred in pembrolizumab monotherapy in patients with melanoma while comparing ORR assessed by RECIST 1.1 vs iRECIST (Hodi FS, 2016). This study would explore the rate of pseudo-progression in NT-I7 plus pembrolizumab assessed by iRECIST 1.1.

In the phase 2a, Go/No Go decision for Arms I, II, III, IV, and V will be based on iRECIST, since iRECIST assessment starts after 1st PD defined by RECIST 1.1.

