	
Biomarker Cohort:
 
 
• To assess the safety and tolerability of NT-I7 in combination with pembrolizumab in subjects with CPI-naïve R/R OC
 

Statistical Methods for Efficacy Analysis	
Primary: ORR will be considered a primary efficacy endpoint and estimated using exact confidence intervals based on the binomial distribution (Clopper-Pearson intervals). A test from the Simon minimax design for null hypothesis ORR proportion in the arm population 4% vs alternative hypothesis 21% will be conducted in each arm at 1-sided alpha = 0.025 and the p-value reported.
 
Arms I, II, III, IV, and V for the Phase 2a study stage will follow the Simon's two-stage minimax design in each arm and has 5 arms. Each arm will enroll 17 evaluable subjects in Stage 1 and, if the Go/No Go criterion is met, an additional 8 evaluable subjects in Stage 2 for a total of 25 evaluable subjects/arm. Exact 95% binomial Clopper-Pearson confidence interval estimates of ORR for arms I, II, III, IV, and V are planned to support the primary hypothesis tests. Enrolment of up to 30 subjects per arm is planned to account for non-evaluable subjects and dropouts. Approximately 210 subjects are planned for the Phase 2a study stage.
 
Note: In addition to the primary analyses on the population of evaluable subjects for the primary endpoint, exploratory analyses will also be presented on the population of all subjects enrolled and treated on study.
 
Secondary:
 
 
• Duration of response (DoR) for the responders in each individual arm, is defined as the time from the first occurrence of a documented objective response to the time of the first documented disease progression or death from any cause, whichever occurs first, per RECIST 1.1 as determined by the investigator. DoR will be assessed statistically via Kaplan-Meier methods and presented descriptively for the responders. Comparative assessments are not planned on this endpoint.
 
• Disease Control Rate (DCR) for each individual arm, is defined as proportion of subjects with a best overall response of CR, PR or SD, per RECIST 1.1 as determined by the investigator. DCR will be assessed statistically via Fisher Exact tests supported by Clopper-Pearson confidence intervals; all analyses will be interpreted descriptively. Comparative assessments are not planned on this endpoint.
 
• Progression Free Survival (PFS) for each individual arm, is defined as the time from the first study treatment (Cycle 1, Day 1) to the first occurrence of progression or death from any cause,
 

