3.3 Efficacy Evaluatable Analysis Set

The efficacy evaluable analysis set will include all subjects who have received at least one dose of both the study medication (NT-I7 and Pembrolizumab) and have an evaluable baseline and at least one evaluable post-baseline assessment of tumor response.

This analysis set will be used as the primary analysis set for all efficacy analysis.

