4.9.2.2 Best Overall Response per iRECIST

BOR will be derived based on all overall visit response per subject. The iRECIST assessment has the following possible response categories: iCR, iPR, iSD, immune-Unconfirmed PD (iUPD), immune-Confirmed PD (iCPD) or immune-Not Evaluable (iNE). The iRECIST criteria is similar to RECIST v1.1 but for PD, iRECIST requires an evaluation of PD to be confirmed at subsequent assessment. For purposes of iRECIST assessment, the first visit showing PD according to RECIST v1.1 will be assigned as Immune-Unconfirmed PD (iUPD) at this visit. Additional imaging for confirmation should be scheduled 4 to 8 weeks from the imaging on which iUPD is seen. This may correspond to the next visit in the original visit schedule. The assessment of the subsequent confirmation imaging proceeds in an identical manner, with possible outcomes of iCPD, iUPD, and iSD/iPR/iCR.

BOR (when confirmation required) per iRECIST will be derived as follows:

- BOR follows the same rules as table 3 per RECIST for confirmation of iCR/iPR, and iSD (meet the minimum criteria), except PD in column response at subsequent

timepoint in table 3 per RECIST is considered as iUPD and should be confirmed by iCPD.

- BOR of iPd (iCPD>iUPD):
 - If subjects did not meet BOR of iCR/iPR, and iSD, BOR for iCPD (time point iUPD must be confirmed by timepoint iCPD no less than 4 weeks per iRECIST) can be achieved as order of iUPD followed by iCPD without interruption of iCR, iPR, iSD.
 - If above scenarios are not achieved, BOR is identified as iUPD.
- BOR of NE refers to no baseline or no postbaseline assessments or all postbaseline assessments are NE.
- BOR of Unknown refers to unconfirmed iCR/iPR or early iSD <4 weeks from first dose date.

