6. CHANGES FROM ANALYSIS PLANNED IN THE PROTOCOL

Analysis is added:

- Exploratory analysis of pre- and on-treatment tumor biopsy samples from the same organ will be performed and compared between responders vs. non-responders and PD vs. non-PD to help elucidate changes in TILs, PD-L1 expression, and TME biomarkers that may be correlated with treatment response.

Analyses are excluded:

- Expression of IFN- γ and associated inflammatory gene expression in the TME.
- Changes in peripheral blood biomarkers, including but not limited to immunophenotyping and inflammatory mediators, will be analyzed in association with 1) the incidence of AEs and 2) as surrogated markers of response, TME changes and TIL infiltration.

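### The protocol announces an exploratory all-treated response rate; the SAP specifies ORR and iORR only in the scan-evaluable set and does not list the omission

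*SAP*

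**What the plan says.** **Protocol.** Section 15.1 takes as evaluable the treated subjects whose data allow ORR to be calculated, and plans up to 30 enrolled per arm so that 25 are evaluable. In section 15.5, a note under the primary ORR method says that, besides the primary evaluable analysis, "exploratory analyses will also be presented on the population of all subjects enrolled and treated on study". The Analysis Populations row of the same table is softer: it permits, but does not require, some efficacy analyses to be rerun on all subjects as treated.

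**SAP.** Section 3.3 limits the efficacy evaluable set to subjects who received both drugs and who "have an evaluable baseline and at least one evaluable post-baseline assessment of tumor response". Section 4.9.3 then states: "ORR per RECIST 1.1 is defined as the proportion of subjects with confirmed CR or confirmed PR as BOR in efficacy evaluable analysis set". The same set is used for iORR. Section 4.9 describes efficacy as based primarily on this set but names no second one. The safety analysis set, which is the all-treated population, is assigned to safety, disease history, prior therapy, exposure, biomarker and anti-drug-antibody summaries, and to no response rate. Section 6 has a list headed "Analyses are excluded"; it holds two biomarker items and says nothing about an all-treated ORR.

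**The concern.** The first scheduled scan is at week 6 (SAP 4.9.1). A treated subject who dies or leaves before any evaluable scan drops out of the denominator, and another subject can be enrolled to bring the evaluable count to 25. Such a subject cannot be a confirmed responder, so leaving the subject out can only raise the observed rate. In relapsed or refractory pancreatic, small cell lung and similar cancers, early loss is unlikely to be unrelated to outcome. In an uncontrolled trial judged on response rate, the all-treated figure is the usual way to see how much this matters. The protocol planned to show it. A programmer working from the SAP would have no population, no rule for unscanned subjects and no table for it.

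**Working it through.** **Inputs.** Null ORR 4%, alternative 21%; 17 + 8 = 25 evaluable; stop at 0 responses in Stage 1; up to 30 enrolled (Protocol 15.1 and 5.4). One-sided alpha 0.025 (Protocol 15.1; SAP 4.9.3: "Arm I, II, III, IV, IVa, V, and Va at 1-sided alpha = 0.025 and the p-value reported"). The final cut-off is not stated and is derived here.

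**The plan's own figure.** Protocol 15.1: "This will provide an estimated 80% power per selected arm in the Phase 2a stage of the study". With success defined as at least c responses among 25 and continuation after at least 1 of 17:

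P(success) = Σ over x = 1 to 17 of P(X1 = x) · P(X2 ≥ c − x), where X1 ~ Bin(17, p) and X2 ~ Bin(8, p).

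| c | P(success) at 4% | P(success) at 21% |
|---|---|---|
| 3 | 0.0749 | 0.916 |
| 4 | 0.0164 | 0.8001 |
| 5 | 0.0028 | 0.627 |

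Only c = 4 meets both alpha ≤ 0.025 and power ≥ 80%. The stated 80% is reproduced, and the lowest positive result is 4/25.

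**All-treated denominator.** Let k be the treated, non-evaluable subjects, counted as non-responders, so n = 25 + k. The allowance gives k = 0 to 30 − 25 = 5.

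- One-sided p = P(X ≥ x | n, 0.04) = 1 − Σ over i = 0 to x − 1 of C(n, i) · 0.04^i · 0.96^(n − i).
- For 4/25: 1 − (0.3604 + 0.3754 + 0.1877 + 0.0600) = 0.0165. The two-stage value is 0.0164.
- For 4/30: 1 − (0.2939 + 0.3673 + 0.2219 + 0.0863) = 0.0306.
- Clopper-Pearson limits: lower = Beta(0.025; x, n − x + 1), upper = Beta(0.975; x + 1, n − x).

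| Result | k | ORR | 95% CI | p vs 4% |
|---|---|---|---|---|
| 4/25 | 0 | 16.0% | 4.5–36.1% | 0.0165 |
| 4/26 | 1 | 15.4% | 4.4–34.9% | 0.0189 |
| 4/27 | 2 | 14.8% | 4.2–33.7% | 0.0215 |
| 4/28 | 3 | 14.3% | 4.0–32.7% | 0.0243 |
| 4/29 | 4 | 13.8% | 3.9–31.7% | 0.0274 |
| 4/30 | 5 | 13.3% | 3.8–30.7% | 0.0306 |
| 5/25 | 0 | 20.0% | 6.8–40.7% | 0.0028 |
| 5/30 | 5 | 16.7% | 5.6–34.7% | 0.0063 |

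The 0.025 line is crossed only at exactly 4 responders with k = 4 or 5.

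**Arms already reported.** Protocol 2.3 gives iRECIST responders of 3/27 in Arm IV and 2/26 in Arm V. Against 4% these give p = 0.092 and p = 1 − 0.3460 − 0.3748 = 0.28. Neither is below 0.025, so a larger denominator changes no conclusion there.

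**The case against.** Several points on the other side stand.

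- **The commitment is exploratory and mixed.** One place in Protocol 15.5 says such analyses will be shown; another says only that a subset may be repeated. The opening of Protocol section 15 sends changes to exploratory analyses to the clinical study report, so an entry in SAP section 6 is good practice rather than a stated requirement. Even so, the SAP takes up neither wording, and section 6 exists to record this kind of change.
- **The rate can be rebuilt.** Barring a responder who received only one drug, the numerator is the same in both sets. SAP 4.1 reports the size of each set and the reasons for discontinuation, so a careful reader could derive the all-treated rate. That softens the point, but it leaves the check to the reader.
- **The excluded group may be small.** SAP 3.3 asks for any evaluable post-baseline assessment, not the week-6 scan. Imaging may be done earlier if clinically indicated, and Protocol 13.3 asks for a scan at treatment discontinuation. Many early progressors will be scanned and counted as non-responders.

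Three stronger readings are tempting and are not supported.

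- A reader might infer that the SAP omission lets an arm succeed by replacing unscanned subjects. The evaluable-only primary test and the 30-for-25 allowance both come from the protocol; the omission removes only the check on their effect.
- A reader might infer that the primary test exceeds its alpha. If the true all-treated ORR were 4% and 5 of 30 went unscanned, the evaluable rate would be 4% × 30/25 = 4.8% and the chance of at least 4/25 would be 0.0298. That applies the null to all treated subjects, whereas the protocol's primary test is on evaluable subjects, and it assumes the full allowance is used.
- A reader might take the rule "BOR of NE refers to no baseline or no postbaseline assessments or all postbaseline assessments are NE" (SAP 4.9.2.2) as a leftover, since such subjects cannot be in the evaluable set. SAP 4.12 summarises biomarkers by response status in the safety set, so the category has a use.

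**Conclusion.** The point holds as a gap between the documents: an exploratory all-treated analysis of the primary endpoint is announced in the protocol, is not specified in the SAP, and is not recorded as dropped. It removes a planned check on upward bias; it does not invalidate the primary analysis. The point estimate can fall from 16.0% to at most 13.3% for an arm with 4 responders, and the comparison with 0.025 changes only at exactly 4 responders with 4 or 5 non-evaluable subjects. Setting an exploratory result against 0.025 serves here only to show scale.

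This rests on four assumptions: the cut-off of 4/25 is the one the design parameters imply; unscanned subjects are non-responders; all non-evaluable subjects were treated, though the allowance also covers dropouts; and their number lies in the planned range of 0 to 5, since the documents give no actual count.

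**What to change.** Add to SAP 4.9.3, for each Phase 2a arm, an exploratory ORR and iORR with exact 95% Clopper-Pearson interval in the safety analysis set. Count a best overall response of NE, Unknown or missing as non-response, and state this for RECIST 1.1 as well as iRECIST, because the rule for subjects without post-baseline assessments now stands only in the iRECIST subsection. Show the result beside the evaluable one, with the number of non-evaluable subjects and the reasons (death, clinical progression, withdrawal, other). Keep the evaluable set primary. Reconcile the two statements in Protocol 15.5 on whether the all-treated analysis is required or optional. If the sponsor prefers not to run it, list it in SAP section 6 with the reason.

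The cost is SAP wording and one extra table row per arm, from data already collected. The downside for the sponsor is that a lower figure may stand beside the headline ORR.

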--	--

	
Q3W for this study.
 
Subjects are required to complete Cycle 1 to be considered evaluable for MTD determination unless discontinuation occurred due to a DLT (i.e., in the dose-determining set).
 
Once the RP2D has been selected, the study will proceed to the Dose Expansion Phase (Phase 2a) to further evaluate RP2D in a larger number of subjects and selected tumor types as described. In the event of unacceptable toxicity in the expansion phase, a lower dose will be explored.
 
Dose Expansion Phase (Phase 2a):
 
The selected arms in Phase 2a, arms I, II, III, IV, and V will follow the Simon's two-stage minimax design in each arm, and 5 arms are planned:
 

○ Arm I : CPI-treated R/R TNBC

○ Arm II : CPI-treated R/R NSCLC

○ Arm III : CPI-treated R/R SCLC

○ Arm IV : CPI-naïve R/R MSS-CRC

○ Arm V : CPI-naïve R/R PC

 
In Stage 1 for arms I, II, III, IV, and V, up to 17 evaluable subjects will be enrolled and treated per arm. If at least one subject achieves objective response (complete response [CR] or partial response [PR]) in an arm, that arm may be expanded by enrolling up to 8 evaluable additional subjects in Stage 2. Study enrollment will continue while the first 17 possible evaluable subjects are undergoing evaluation to confirm response. If no objective response is observed in an arm during Stage 1, further enrollment will be stopped in that arm.
 
Arms IVa (MSS-CRC), Va (PC), and the Biomarker Cohort will not follow the Simon's two-state minimax design. Arms IVa and Va will enroll up to 25 evaluable subjects per arm. NT-I7 will be administered at 1200 ug/kg IM Q6W, with Pembrolizumab fixed dose at 200 mg IV Q3W.
 

○ Arm IVa : CPI-naïve R/R MSS-CRC

○ Arm Va : CPI-naïve R/R PC

 
Biomarker Cohort:
 
The Biomarker Cohort is designed to assess the correlation between tumor infiltrating lymphocytes (TILs) and clinical benefits of NT-I7 in combination with pembrolizumab in subjects with CPI naïve R/R Ovarian Cancer (OC). Up to 10 evaluable subjects will be enrolled to obtain at least 4 pairs of evaluable

--	---

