1.3 Study Design

1.3.1 Overall Design

This is a multicenter, open-label Phase 1b/2a study of NT-I7 in combination with pembrolizumab. The study will include a dose escalation phase (Phase 1b) followed by a dose expansion phase (Phase 2a) and a Biomarker cohort (See study design in Figure 1).

The Phase 1b is designed to assess the safety and tolerability, including determination of the MTD and/or the RP2D, of NT-I7 in combination with pembrolizumab in subjects with advanced solid tumors. The Phase 1b will follow the standard 3+3 study design. Three DLs of NT-I7 are planned [DL 1 (480 µg/kg IM Q6W), DL 2 (960 µg/kg IM Q6W), and DL 3 (1200 µg/kg IM Q6W)], and up to 18 subjects will be enrolled (up to 6 subjects per DL). Doses may be de-escalated to one or two levels (e.g., 360 or 240 µg/kg IM Q6W) depending on the pre-defined DLT criteria. Pembrolizumab dose is fixed at 200 mg IV Q3W for all DLs. Upon completion of Phase 1b, the MTD was not reached. There was 1 DLT (Grade 3 ALT increased) observed at the highest DL tested (1,200 µg/kg; n=6 patients). The RP2D was determined to be NT-I7 1,200 µg/kg (IM Q6W) and pembrolizumab 200 mg (IV Q3W).

For Phase 2a, selected arms I, II, III, IV, and V will follow the Simon's minimax two-stage design which include the following indications: CPI treated R/R tumors (TNBC, NSCLC, SCLC), and CPI naïve R/R tumors (MSS-CRC and PC). Each arm will enroll up to 17 evaluable subjects in Stage 1 and, if the Go/No Go criterion is met, an additional 8 evaluable subjects will be enrolled in Stage 2 for a total of 25 evaluable subjects per arm. Exact 95% binomial Clopper-Pearson confidence interval (CI) estimates of ORR from each arm is planned to support the primary hypothesis tests. Study enrollment will continue while the first 17 subjects are undergoing evaluation to confirm response. Enrollment of up to 30 subjects per arm is planned to account for non-evaluable subjects and dropouts. Approximately 210 subjects are planned in total for the Phase 2a. Subjects in the Phase 2a will be treated at the RP2D for the combination as determined in the Phase 1b.

[figure not shown]
Arms IVa, Va, and the Biomarker Cohort will not follow the Simon's minimax two-stage design.

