1.3.3 Dose Expansion (Phase 2a)

Subjects enrolled into the study during the dose expansion phase (Phase 2a) will be treated at the RP2D, which was determined to be 1200 µg/kg IM Q6W. Certain indications may be selected to expand in the expansion phase based on the emerging data.

For Phase 2a, Arms I, II, III, IV, and V will follow the Simon's two-stage minimax design. Arms IVa, Va, and the Biomarker Cohort OC will not follow the Simon's two-stage minimax design.

- Arm I: CPI treated R/R TNBC
- Arm II: CPI treated R/R NSCLC
- Arm III: CPI treated R/R SCLC
- Arm IV: CPI naïve R/R MSS-CRC
- Arm IVa: CPI naïve R/R MSS-CRC

- Arm V: CPI naïve R/R PC
- Arm Va: CPI naïve R/R PC
- Biomarker Cohort: CPI naïve R/R OC

In Stage 1, up to 17 evaluable subjects per arm will be enrolled and treated. If at least one subject achieves objective response (immune-complete response [iCR] or immune-partial response [iPR]) per iRECIST in an arm, that arm may be expanded by enrolling up to 8 evaluable additional subjects in Stage 2. Study enrolment will continue while the first 17 subjects are undergoing evaluation to confirm response. If no objective response is observed in an arm during Stage 1, further enrolment will be stopped in that arm.

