1.3.6 Schedule of Procedures and Assessments

The schedule of procedures and assessments is described in protocol section 7. See Figure 2 for the treatment schema.

Figure 2 Treatment Schema**1.4 Sample Size Calculation**

The Phase 1b will follow the standard 3+3 study design. Three DLs of NT-I7 are planned [DL 1 (480 µg/kg IM Q6W), DL 2 (960 µg/kg IM Q6W), and DL 3 (1200 µg/kg IM Q6W)], and up to 18 subjects will be enrolled.

ORR assessed by RECIST 1.1 and iRECIST will be considered as primary efficacy endpoints in each Phase 2a arm and estimated using exact CIs based on the binomial distribution (Clopper-Pearson intervals) from the evaluable subjects for selected arms. All subjects treated in the study with data available for the calculation of the primary endpoint ORR will be considered evaluable. A test from the Simon minimax design for null hypothesis ORR proportion 4% vs alternative hypothesis 21% in the

arm population will be conducted in selected arms at 1-sided alpha = 0.025 and the p-value reported.

Arms I, II, III, IV, and V of the Phase 2a study stage will follow the Simon's two-stage minimax design. Each arm will enroll 17 evaluable subjects in Stage 1 and, if the Go/No Go criterion is met, an additional 8 evaluable subjects in Stage 2 will be enrolled for a total of 25 evaluable subjects/arm. This will provide an estimated 80% power per selected arm in the Phase 2a stage of the study for the primary hypothesis test using the Simon minimax design. Exact 95% binomial Clopper-Pearson CI estimates of ORR from each arm is planned to support the primary hypothesis tests.

Arms IVa, and Va of the Phase 2a study stage will not follow the Simon's two-stage minimax design.

Enrolment of up to 30 subjects per arm (I, II, III, IV, IVa, V, and Va) is planned to account for non-evaluable subjects and dropouts. Up to 238 subjects (up to 18 subjects in Phase 1b, up to 210 subjects in all arms of Phase 2a, and up to 10 subjects in the Biomarker Cohort) are planned to be enrolled in the study.

It has been reported that approximate 7% of pseudo-progression occurred in pembrolizumab monotherapy in patients with melanoma while comparing ORR assessed by RECIST 1.1 vs iRECIST (Hodi FS, 2016). This study will also explore the rate of pseudo-progression in NT-I7 plus pembrolizumab assessed by iRECIST.

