2.7 Testing Hypotheses

Arms I, II, III, IV, and V of the Phase 2a study stage will follow the Simon's two-stage minimax design. A test from the Simon minimax design for null hypothesis ORR proportion 4% vs. alternative hypothesis 21% in the arm population will be conducted in selected arms at 1-sided alpha = 0.025.

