2.9 Timing of Analysis

2.9.1 Interim Analysis

In Phase 1b there is a safety interim analysis after each DL to determine the dosing for the next subject.

In Phase 2a, Arms I, II, III, IV, and V will have a futility interim analysis per the Simon's two-stage minimax design at 17 evaluable subjects based on ORR assessed by iRECIST. If at least one subject achieves objective response (iCR or iPR) in an arm, that arm may be expanded by enrolling up to 8 evaluable additional subjects in Stage 2. Study enrollment will continue while the first 17 possible evaluable subjects are undergoing evaluation to confirm response. If no objective response is observed in an arm during Stage 1, further enrollment will be stopped in that arm.

In Phase 2a, Go/No Go decision for Arms I, II, III, IV, and V will be based on iRECIST, since iRECIST assessment starts after 1st PD defined by RECIST 1.1.

An interim analysis will not be performed for IVa, Va, and the Biomarker Cohort.

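### SAP 4.9.3 orders a Simon minimax test with a p-value in Arms IVa and Va, which both documents place outside the Simon design; the p-value would not match how those arms are sampled

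*SAP*

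**What the plan says.** SAP 4.9.3 calls for a test taken from the Simon minimax design, null 4% against alternative 21%, for ORR and iORR. It says the test "will be conducted in each Phase 2a Arm: Arm I, II, III, IV, IVa, V, and Va at 1-sided alpha = 0.025" and that the p-value is reported. The same section orders exact two-sided 95% Clopper-Pearson intervals.

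The SAP's design sections put two of those seven arms outside the design:

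- SAP 1.3.1: "Arms IVa, Va, and the Biomarker Cohort will not follow the Simon's minimax two-stage design".
- SAP 1.3.3: "Arms IVa, Va, and the Biomarker Cohort OC will not follow the Simon's two-stage minimax design".
- SAP 1.4: "Arms IVa, and Va of the Phase 2a study stage will not follow the Simon's two-stage minimax design".
- SAP 2.9.1: "An interim analysis will not be performed for IVa, Va, and the Biomarker Cohort".

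The protocol agrees in its synopsis (1.1) and in 5.1, 5.4 and 15.3. On size, the synopsis says "Arms IVa and Va will enroll up to 25 evaluable subjects per arm", with no division into stages.

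On which arms are tested, the text is not uniform. SAP 2.7 names Arms I to V as the Simon arms and says the test "will be conducted in selected arms at 1-sided alpha = 0.025". Protocol 15.1 likewise says it "will be conducted in selected arms at 1-sided alpha = 0.025 and the p-value reported". Neither defines the selection. In Protocol 15.5, the efficacy-methods row calls for the test in every arm. The next paragraph of that row ties both the Simon design and the intervals supporting the hypothesis tests to Arms I to V. The analysis-populations row of 15.5 plans a descriptive analysis of Arms IVa and Va once enrollment ends.

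**The concern.** A p-value is a tail probability under a particular sampling plan. The Simon plan for Arms I to V stops an arm with no responder among the first 17 evaluable subjects, and its p-value leaves out every path on which responders appear only after subject 17. Arms IVa and Va have no Stage 1 and no stop, so those paths can occur. A Simon p-value there is computed for a design that was not run, and it comes out slightly too small.

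A programmer cannot satisfy SAP 4.9.3 together with SAP 1.3.1, 1.3.3 and 1.4 as written, because no single-stage method is named. The study report could then print a p-value under the wrong label for two arms, and a reader would not know whether those arms were meant to be tested or described.

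**Working it through.** **Inputs.** Null 4%, alternative 21%, one-sided alpha 0.025 (SAP 4.9.3, Protocol 15.1). Stages of 17 and 8, total 25 (Protocol 15.1). Stop at 0 responders in Stage 1 (Protocol 5.4, SAP 1.3.3). Arms IVa and Va: up to 25 evaluable (Protocol 1.1), with up to 30 enrolled (SAP 1.4). Neither document prints a final cut-off, so it is derived here.

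**Step 1: reproduce the plan's design.** An exact search for the smallest total sample size, and then the smallest expected size under the null, with alpha at most 0.025 and power at least 0.80, returns 17 in Stage 1, stop at 0, total 25, reject at 4 or more. Attained alpha is 0.0164, power 0.8001, and the chance of stopping early under the null is 0.96^17 = 0.4996. The stated design is sound for Arms I to V.

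**Step 2: p-values for s responders in 25, at a 4% rate.** X1 counts responders in the first 17 and X2 in the next 8.

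- Simon: P(X1 ≥ 1 and X1 + X2 ≥ s)
- Single stage: P(X ≥ s), with X binomial (25, 0.04)
- Difference: P(X1 = 0) × P(X2 ≥ s) = 0.4996 × P(X2 ≥ s)

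For s = 1, P(X2 ≥ 1) = 1 − 0.96^8 = 0.2786, so the difference is 0.4996 × 0.2786 = 0.139. For s = 2, P(X2 ≥ 2) = 0.0381, giving 0.4996 × 0.0381 = 0.019.

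| Responders of 25 | Simon | Single-stage exact |
|---|---|---|
| 1 | 0.500 | 0.640 |
| 2 | 0.245 | 0.264 |
| 3 | 0.0749 | 0.0765 |
| 4 | 0.0164 | 0.0165 |
| 5 | 0.0028 | 0.0028 |

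Power of rejecting at 4 or more of 25 is 0.800 (Simon) and 0.801 (single stage).

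**Step 3: outcomes with no Simon p-value.** If all k responders fall after subject 17, a Simon arm would already have stopped. Given k responders among 25, the chance of this is C(8,k)/C(25,k): 32% for 1, 9.3% for 2, 2.4% for 3 and 0.6% for 4.

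**Step 4: does any decision change?** The first stage is kept at 17 and the total is varied. P-values are Simon, then single stage.

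| Evaluable | 4 responders | 5 responders | Cut-off at 0.025, both methods |
|---|---|---|---|
| 25 | 0.0164, 0.0165 | 0.0028, 0.0028 | 4 |
| 26 | 0.0188, 0.0189 | 0.0033, 0.0033 | 4 |
| 27 | 0.0213, 0.0215 | 0.0039, 0.0040 | 4 |
| 28 | 0.0240, 0.0243 | 0.0046, 0.0047 | 4 |
| 29 | 0.0269, 0.0274 | 0.0054, 0.0054 | 5 |
| 30 | 0.0299, 0.0306 | 0.0063, 0.0063 | 5 |

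The two methods agree at every size. The cut-off does move from 4 to 5 at 29 evaluable, so any test has to use the actual number evaluable.

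**The case against.** The best defence is that not following the two-stage design concerns enrollment and stopping, while SAP 4.9.3 may borrow only the hypotheses and the alpha. Testing a single-stage arm against the same 4% null is legitimate. The protocol gives this some support. Section 15.5 calls for the test in every arm, 15.1 makes ORR a primary endpoint in each Phase 2a arm, and 2.3 says these arms were added to help establish a clinically significant response rate. Listing all seven arms by name also looks deliberate.

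Much of this stands. It shows that a test may be intended, so a reader who infers that the tests are a plain mistake goes beyond the documents. The descriptive-analysis sentence in Protocol 15.5 does not settle it either, since it does not say that the analysis is only descriptive. For the same reason, the silence of SAP Section 6 is not clearly an omission. What the defence does not rescue is the method: SAP 4.9.3 asks for a test from the Simon design and offers no single-stage alternative.

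A reader might also infer a multiplicity fault, because colorectal and pancreatic cancer would each be tested twice. The documents do not support that. Neither sets an error limit per tumour type, and Protocol 15.5 openly plans no adjustment. Protocol 2.3, in the version on which the SAP is based, already reports Arms IV and V at 3/27 and 2/26 by iRECIST. Their single-stage p-values are 0.092 and 0.279, short of rejection.

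Those denominators also show that Arms IV and V did not end at exactly 25. Restricting the Simon label to Arms I to V does not by itself say how a p-value is computed at another size. That is a separate matter.

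**Conclusion.** The contradiction is real and minor. As written, the p-value for Arms IVa and Va would not match their sampling plan. At 25 evaluable the discrepancy is 0.139 at 1 responder, 0.019 at 2, and 0.002 or less from 3 upward. A reader might infer that a conclusion could flip; it could not, since both methods reject at the same count for every size from 25 to 30. What needs settling is the method, its label, and whether these arms are tested or described. The documents leave the last question open.

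The figures rest on a cut-off derived from the stated design, a first stage of exactly 17, and independent responses at a common 4% rate within an arm.

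**What to change.** In SAP 4.9.3, limit the Simon test to Arms I, II, III, IV and V. For Arms IVa and Va, choose one of two options:

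- Report ORR and iORR with the exact 95% Clopper-Pearson interval already ordered in SAP 4.9.3, interpreted descriptively. Little is lost: at 4/25 the interval runs from 4.5% to 36.1% and excludes 4%, and at 3/25 it runs from 2.5% to 31.2% and does not.
- If a test of the 4% null is intended, name it a single-stage exact binomial test at the actual number evaluable.

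Then align the arm wording in Protocol 15.5, Protocol 15.1 and SAP 2.7 with that choice, naming the arms.

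The cost is a sentence or two in SAP 4.9.3 and a wording alignment in three other places. Two arms' p-values are dropped or relabelled. Data collection, sample size and the Go/No Go rule do not change.
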